11.0 STATISTICAL ANALYSIS PLAN

11.1 Study Design and Primary Endpoint

This is a single arm Phase II study to evaluate the efficacy of consolidation MK-3475 in extensive stage SCLC patients following completion of 4 cycles of chemotherapy with cisplatin or carboplatin and etoposide and whose disease has either responded or stabilized following chemotherapy. We propose a single arm study since the standard initial therapy for SCLC is well established for the last 20 years and the median PFS following such induction therapy is well defined, making a randomized study with control arm less necessary.

The primary endpoint is PFS with RECIST criteria defined as duration of time from registration to time of progression. Patients register after the induction chemotherapy is completed and have achieved stable or responding disease. Patients who die without reported prior progression will be considered to have progressed on the day of their death. Patients who did not progress will be censored at the day of last tumor assessment. PFS has been the primary endpoint in most maintenance trials conducted in SCLC patients to date.

11.2 Sample Size and Accrual Rate:

The median PFS in SCLC patients who have stable or responding disease following initial chemotherapy is approximately 2 months. We expect that the experimental treatment will improve the median PFS 50% to 3 months. Assume an exponential and one-sided alpha 0.05, 40 patients accrued in 18 months with minimum follow-up time 6 months will achieve 80% power to test the null hypothesis that median PFS is 2 months versus the alternative of 3 months.[PASS14.0.7] (29). In this protocol, we assume about 10% of patients will be ineligible. Thus, a total of 45 will be enrolled to study. To assess the efficacy, we will follow each patient to at least 6 months or progression.

It is estimated that approximately 28 patients per year should be accrued once the study is open at all sites (4-5 sites). Thus, the accrual duration will be about 18 months and the study duration is 24 months including the 6 months follow-up. All patients will be followed for PFS and OS to evaluate the clinical benefit of MK-3475.

11.3 Analysis plan for primary and secondary endpoints

The primary endpoint, PFS, will be estimated with the standard Kaplan-Meier method, from which summary statistics of interest (median, 1-year rate, etc.) will be derived. Both point and 95% confidence interval estimates of PFS will be calculated. In this trial we will also assess PFS using modified criteria as well. It is well recognized that patients treated with immune therapy may have pseudo progression or can have delayed response. The modified PFS requires RECIST defined progression on 2 sequential scans at least 4 weeks apart for definition of progression. Overall survival is defined as the time from start of treatment to time of death. If the patient is lost to follow-up, survival will be censored on the last date the patient was known to be alive. All time-to-event endpoints will be estimated using standard Kaplan-Meier methods, from which the median and confidence interval will be calculated. Point and exact confidence interval estimates will be calculated for the toxicities and response rates. Cox model will be used to evaluate the association between time to event outcomes and covariates such as PD-L1 status and CTCs.

PD-L1 (yes/no) in tumor tissue and circulating tumor cells (CTCs) will be measured and their association will be studied with logistic regression. We will explore associations between PD-L1 and PFS, modified PFS, and OS using the Cox model. If biopsy samples are 15 patients or less, statistical analysis will be descriptive.

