3.2 Secondary Objective(s) & Hypothesis(es)

1. To assess modified PFS in all patients enrolled (**see section 10.2 for definition**).
2. To assess overall survival of patients enrolled on the trial.
3. To assess PD-L1 expression in archival tumor tissues and in circulating tumor cells (CTCs) and correlate the expression to RECIST defined PFS.

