Patients were required to submit a newly obtained tumor biopsy prior to initiating therapy with MK-3475 to evaluate the tumors for expression of PD-L1, the presumptive predictive biomarker of MK-3475, using an immunohistochemistry assay. A modified H-score scoring system of PD-L1 expression was established for NSCLC by analyzing tumor specimens from resected NSCLC specimens. This scoring system was then applied to the samples from these NSCLC patients. A receiver-operating characteristics curve was constructed from the data and the Youden Index identified from that analysis to help determine a preliminary cut point. As stated above, preliminary data suggest higher levels of PD-L1 expression are associated with increased activity. Additional data are required to define the optimal PD-L1 cut point.

The safety of MK-3475 was characterized in the 1-month repeat-dose toxicity study in cynomolgus monkeys when administered as IV doses of 6, 40 or 200 mg/kg once a week (a total of five doses) and in the 6-month repeat-dose toxicity study in cynomolgus monkeys when administered as IV doses of 6, 40 or 200 mg/kg every other week (a total of 12 doses). MK-3475 was well-tolerated in cynomolgus monkeys with a

systemic exposure (AUC) of up to approximately 170,000 $\mu\text{g}\cdot\text{day}/\text{mL}$ over the course of the 1-month study, and with a systemic exposure (AUC) of up to approximately 67,500 $\mu\text{g}\cdot\text{day}/\text{mL}$ over the course of the 6-month study. No findings of toxicological significance were observed in either 1-month or 6-month toxicity study with MK-3475 and the NOAEL was ≥ 200 mg/kg. In addition, no findings of toxicological relevance were observed in the in vitro tissue cross-reactivity study using human and cynomolgus monkey tissues. There were no nonclinical findings that would preclude testing of MK-3475 in clinical trials.

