4.2.3.1 Biomarker Research

Emerging data suggests that expression of PD-L1 on the tumor may predict for benefit from the MK-3475 and other anti-PD-1. Benefit has also been observed in patients whose tumors don't express PD-L1 but the percentage of such patients who benefit is far less. This difference in efficacy with anti- PD-1 drugs has been observed across tumor types. The rate of PD-L1 expression in SCLC is not well defined. We therefore plan to assess the expression of PD-L1 in tumors of patients enrolled on the trial and correlate the presence of PD-L1 with efficacy end points.

Tumor content in diagnostic biopsies is likely to be limited in SCLC patients. In addition, biopsy of residual tumor following initial chemotherapy may be challenging. Circulating tumor cells (CTCs) hold great promise as a readily available source material that can offer real-time insight into a tumor's genomic architecture. CTCs can be detected in small cell lung cancer patients and appear to have prognostic importance (20, 21). We propose to collect CTCs and assess PD-L1 expression in CTCs an attempt to correlate PD-L1 expression in CTCs with patient's primary tumor and with efficacy parameters.

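### Tissue PD-L1 is coded yes/no with no definition of yes; adding a graded analysis and fixing the threshold in advance would be a cheap improvement

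*Combined protocol and SAP*

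**What the plan says.** The third secondary objective in Section 3.2 is to assess PD-L1 in archival tissue and in CTCs and to "correlate the expression to RECIST defined PFS".

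Section 11.3 gives the only coding, "PD-L1 (yes/no) in tumor tissue", in this sentence: "PD-L1 (yes/no) in tumor tissue and circulating tumor cells (CTCs) will be measured and their association will be studied with logistic regression". The next sentence reads "We will explore associations between PD-L1 and PFS, modified PFS, and OS using the Cox model", and the paragraph before it lists Cox "covariates such as PD-L1 status and CTCs". If there are 15 or fewer biopsy samples, the analysis is descriptive only. No threshold, scoring scale or graded analysis is named. Section 9.0 names the testing laboratory but not what it will report.

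Two background sections bear on the coding:
- Section 4.2.1, MK-3475 (Pembrolizumab), describes a modified H-score established for NSCLC. A ROC curve was built from the NSCLC data and "the Youden Index identified from that analysis to help determine a preliminary cut point". It adds: "Additional data are required to define the optimal PD-L1 cut point".
- Section 4.2.3.1 says "The rate of PD-L1 expression in SCLC is not well defined", and frames the plan as relating the presence of PD-L1 to efficacy.

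Tissue submission is optional (Section 7.1, footnote 8). Section 9.0 says the correlative studies are unlikely to be definitive because numbers are small.

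**The concern.** The objective speaks of expression, and a graded scale for PD-L1 exists in the protocol's own background. The analysis nevertheless names only a two-level variable and leaves the boundary between the levels open. Two things follow.

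First, if risk changes gradually with expression, a split discards information from a sample that is already small: at most 45 patients, and fewer if tissue is missing. A real gradient becomes easier to miss.

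Secondly, a result for an undefined category is hard to interpret or to carry into a later trial, and guiding later biomarker work is the purpose Section 9.0 gives for these studies.

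**Working it through.** **The plan's own figure.** No sample size or power is given for PD-L1. The primary calculation in Section 11.2 reproduces, and it supplies the event probability used below.
- Events needed for median PFS 3 against 2 months, one-sided 0.05, 80% power: (1.645 + 0.842)² / ln(1.5)² = 37.6.
- Event probability with 18 months' accrual, 6 months' minimum follow-up and λ = ln 2/3 = 0.231 per month: 1 − (e^(−6λ) − e^(−24λ))/(18λ) = 1 − (0.2500 − 0.0039)/4.159 = 0.941.
- 37.6/0.941 = 39.97, so 40. Then 40/0.9 = 44.4, so 45.

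**Information kept by a split.** Assume a normal score with a log-linear effect on the hazard. The share kept is the squared correlation between the score and its split, φ(z_p)² / [p(1 − p)], where p is the share positive. At p = 0.5 this is 0.3989²/0.25 = 0.637; at p = 0.1 it is 0.1755²/0.09 = 0.342.

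| Share positive (assumed) | Kept | Lost |
|---|---|---|
| 50% | 0.637 | 36% |
| 30% | 0.576 | 42% |
| 20% | 0.490 | 51% |
| 10% | 0.342 | 66% |

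With tissue on 40 patients (40 × 0.941 = 37.6 PFS events), the split is worth about 24 events at 50% positive, 18 at 20% and 13 at 10%. If the score had 80% power at two-sided 0.05 (an assumed level), the split would have Φ(2.802 × √kept − 1.96): 61%, 50% and 37% respectively.

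**Other shapes.** The same squared correlation, from 2,000,000 simulated scores, with the effect still log-linear:
- No zeros, uniform score, 10% positive: 73% lost.
- Exact zeros, split at zero, positives uniform: 40% lost with 50% zeros and 27% with 90% zeros.
- Exact zeros, positives exponential: 67% lost with 50% zeros and 53% with 90% zeros.
- Exact zeros, positives tightly clustered (mean 5, SD 1): 7% lost with 50% zeros and 4% with 90% zeros.

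If the true effect is a step exactly at the cut, the split loses nothing and the linear score is the less efficient choice, by the same squared correlation.

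**Scale of the sample.** The hazard ratio detectable by a yes/no split (two-sided 0.05, 80% power) is exp[2.802/√(d·p(1 − p))], with d the number of events. With 40 samples it is 2.49 at 50% positive, 3.13 at 20% and 4.58 at 10%. With 16 samples, the fewest the plan would still model, it is 4.24, 6.08 and 11.1.

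**A cut chosen on PFS (hypothetical).** Null simulations searched every split from 20% to 80% for the best log-rank result at a nominal 5%. The false-positive rate was about 33% for a score without ties at n = 20, 30 and 40. It fell to about 20–22% with 50% zeros, 14% with 70% and 7–8% with 80%.

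**The case against.** Section 4.2.3.1 talks about the presence of PD-L1 and contrasts it with tumors that do not express it. Yes/no may therefore simply mean any expression against none, not a tuned cut on a score. That is a fair reading, and it supplies a sensible threshold. Section 11.3 still does not state it, and it does not make a graded analysis redundant.

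It can also be said that the yes/no wording belongs to the tissue–CTC logistic regression, and that its use in the Cox models is inference. This is correct. The reference to PD-L1 status makes binary the likelier reading, but no more than that.

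Feasibility is a further limit. The H-score was established on resected NSCLC specimens, whereas here the tissue is archival and tumor content is expected to be limited. Scores may be missing or mostly zero. This stands, and it is a reason to add the graded model without displacing the binary one.

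Three stronger readings are tempting, and the documents do not support them:
- That the protocol admits no cut point is settled for this disease. The sentence on the optimal cut point concerns NSCLC; on an SCLC cut point the protocol is silent.
- That the split discards a third to two-thirds of the information as a matter of fact. That range needs a normal score, a log-linear effect and 10% to 50% positive, none of which is given.
- That the association will be falsely positive about a third of the time. The ROC and Youden work is background from another trial, and nothing here proposes choosing the threshold on PFS.

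**Conclusion.** The point holds in a limited form. Yes/no is the only coding given for tissue PD-L1, yes is undefined, and the background describes a graded scale that the analysis does not use. Under a normal score and a log-linear effect, the loss is about 36% at 50% positive and 66% at 10% positive. Across the other shapes tried it runs from about 4% to 73%, and it is zero for a step at the cut. The documents do not say which case applies, so the size is unknown. The analysis is exploratory, and no decision rule, error rate or sample size depends on it. This is a low-priority, cheap improvement.

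**What to change.** Three small changes:
- Ask the central laboratory to report the PD-L1 score or percent staining wherever tissue allows, and name the scale in Section 9.0.
- Add to Section 11.3 a Cox model for RECIST PFS with PD-L1 as a continuous or ordinal term, alongside the yes/no analysis. Preferring one as the main analysis is partly a matter of taste; reporting both covers a gradient and a step.
- Define yes in Section 11.3, for example any expression against none, and fix it before scores are linked to outcome. This also closes off a threshold chosen on PFS.

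The cost is a line in the laboratory request and a sentence or two in the SAP, provided the laboratory can score this tissue, which the documents do not confirm. No extra patients or samples are needed. A per-unit hazard ratio is harder to read than a yes/no contrast, and for some samples the score may be unavailable or mostly zero. The rule for 15 or fewer samples can stay as it is.

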5. Patients should undergo CBC with differential count, a multiphasic profile consisting of serum electrolytes, BUN, serum creatinine, AST, ALT, serum bilirubin, alkaline phosphatase, and calcium with each treatment. . Baseline labs should be done within 2 weeks of the first dose of MK-3475. During the trial, laboratory tests can be done within 48 hours of the administration of MK-3475.
6. Patients should undergo Thyroid tests within 2 weeks of the first dose. These should be repeated at least every 4 cycles.
7. Patients should undergo appropriate scans, including brain scan, during screening, to document the status of the patient' cancer. The screening scans should be done within 3 weeks before the first dose of MK-3475. Patients should undergo appropriate scans to restage the patient after every 2 cycles for the first 6 cycles. For the first 6 cycles the re-staging scans should be performed within 1 week of the next cycle. After the first 6 cycles, the scans can be done as often as necessary by the treating physician but should be done at least every 4 cycles.
8. Archival tumor tissue will be retrieved to assess tumor PD-L1 status. Any tissue available should be submitted. Patient will be eligible even if tumor tissue cannot be submitted.
9. Patients will undergo blood collection for Circulating Tumor Cells (CTCs). This can be done on the first day of the first cycle prior to dosing MK-3475. This should also

be done on the first day of the second cycle and first day of the third cycle even if the drug is being held.

10. Patients who have completed 24 months on MK-3475 and stop therapy without progression can be retreated if patient has further progression. Patient will have to meet all original eligibility criteria and will be assessed and managed as a new patient starting on therapy. See section 8.1.6.
11. Every 12 weeks until the start of the next treatment for patient's cancer, disease progression, death, end of study.

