Tumor content in diagnostic biopsies is likely to be limited in SCLC patients. In addition, serial biopsies are challenging in patients with SCLC. Also after completion of chemotherapy, biopsy of residual tumor may be challenging. Circulating tumor cells (CTCs) hold great promise as a readily available source material that can offer real-time insight into a tumor's genomic architecture as well as tumor burden. CTCs can be detected in small cell lung cancer patients and appear to have prognostic importance (20, 21). [name], Director of the Biobanking and Correlative Sciences Core will supervise quantitation of CTCs in patients enrolled on this study. Peripheral blood (8 mL) will be collected into a Cell Search CTC collection tube. Tumor cells are then subject to negative immunomagnetic selection with anti-CD45 antibodies and positive immunomagnetic selection with EpCAM antibodies and fluorescently labeled for quantitation. These fluorescently labeled cells can be stained for PD-L1 for correlation with tumor progression assessment. Alternatively, the immunomagnetic platform allows isolation of EpCAM selected cells from the peripheral blood from which mRNA can be reverse-transcribed for RT-PCR. Using beta-actin as an internal control, mRNA expression levels of target genes can be ascertained. As a correlate to this trial, we will collect blood prior to therapy on the first day of the first cycle, on the first day of second cycle, and first day of the third cycle. After processing, samples will be shipped to the [name] laboratory (see shipping address and conditions below). Both

CTC counts and assessment of PD-L1 protein and mRNA expression in isolated CTCs will be done.

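### Tissue and CTC PD-L1 are to be compared by logistic regression from 16 biopsies upward; if positivity is low or agreement strong, an empty cell is likely and ordinary fitting gives no finite odds ratio

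*Combined protocol and SAP*

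**What the plan says.** Section 11.3 states: "PD-L1 (yes/no) in tumor tissue and circulating tumor cells (CTCs) will be measured", and continues that "their association will be studied with logistic regression". The natural reading is two binary markers, hence a 2x2 table. The only small-sample provision is "If biopsy samples are 15 patients or less, statistical analysis will be descriptive". That rule counts biopsies and does not mention pairs. No exact or penalised fitting is named, and no agreement statistic is planned.

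Other sections bear on how much data there will be:

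- Flow chart notes (section 7.1): "Patient will be eligible even if tumor tissue cannot be submitted".
- Section 9.0: "Tumor content in diagnostic biopsies is likely to be limited in SCLC patients". CTC blood is drawn on day 1 of cycles 1, 2 and 3. Section 11.3 does not say which draw is compared with tissue.
- Section 4.2.3.1: "The rate of PD-L1 expression in SCLC is not well defined". The stated aim is an "attempt to correlate PD-L1 expression in CTCs with patient's primary tumor and with efficacy parameters".
- Section 11.2: 45 patients enrolled, which is the ceiling on pairs.

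Section 9.0 concedes that the correlative work is unlikely to be definitive at this size.

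**The concern.** With a single yes/no predictor, logistic regression is a 2x2 table in another form, and its maximum-likelihood odds ratio exists only if all four cells are occupied. The plan lets modelling begin at a size where that cannot be relied on, and it names no fallback for a sparse table. The risk is greatest when positives are rare or when CTCs track tissue closely. The second case is the one in which the comparison would be most interesting.

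The choice of measure also matters. CTCs are collected partly because tissue is scarce in this disease, so a reader will want to know how often the two sources give the same answer. An odds ratio does not say.

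What is at stake is a usable estimate from an exploratory correlate that is meant to guide later biomarker work.

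**Working it through.** **The plan's own figures.** None is given for this comparison or for the cut-off of 15. The only calculated figure is the primary sample size, and it reproduces. With 37.6 expected events among 40 patients, power is Φ(√37.6 × ln 1.5 − 1.645) = 0.80, and 40/0.9 = 44.4, rounded up to 45. It matters here only as the ceiling on pairs.

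**Inputs.** From the documents: binary markers, modelling from 16 biopsies, at most 45 pairs. Assumed, because the documents are silent: positivity of 10% to 50%, equal in the two sources; association given either by odds ratios of 1, 5 and 15 or by kappa 0.8.

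**Step 1: when the estimate fails.** Write the table as (a, b, c, d): both positive, tissue only, CTC only, neither. The odds ratio is ad/(bc). One zero cell makes it 0 or infinite. A zero row or column means that one marker is constant, and the odds ratio is undefined.

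**Step 2: probability of an empty cell.** For cell probabilities p1 to p4 and n pairs,

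P = Σ(1 − pi)^n − Σ(1 − pi − pj)^n + Σ pk^n,

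with the sums over single cells, over pairs of cells, and over the one cell left when three are empty.

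Worked case: positivity 20%, kappa 0.8, n = 16.

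- Both positive: 0.2² + 0.8 × 0.2 × 0.8 = 0.168. Each discordant cell: 0.032. Both negative: 0.768.
- Singles: 0.832^16 + 2 × 0.968^16 = 0.053 + 1.189 = 1.241 (the fourth term is negligible).
- Pairs: 2 × 0.8^16 + 0.936^16 = 0.056 + 0.347 = 0.403.
- Triples: 0.768^16 = 0.015.
- P = 1.241 − 0.403 + 0.015 = 0.853.

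**Step 3: over the assumed range.** Probability of at least one empty cell:

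| Positivity | 16 pairs, OR 1-15 | 16 pairs, kappa 0.8 | 30 pairs, OR 1-15 | 40 pairs, OR 1-15 | 40 pairs, kappa 0.8 |
|---|---|---|---|---|---|
| 10% | 83-92% | 96% | 52-77% | 34-69% | 75% |
| 20% | 46-59% | 85% | 12-30% | 4-20% | 47% |
| 30% | 24-41% | 76% | 3-11% | 1-4% | 33% |
| 40% | 9-35% | 71% | 1-8% | up to 3% | 26% |
| 50% | 4-33% | 70% | up to 8% | up to 3% | 24% |

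The OR columns span the values at 1, 5 and 15. Between these the probability can dip a little lower: at 30% positivity and 16 pairs it is 20% at an odds ratio of about 2.5. At 45 pairs and kappa 0.8 it is still 19-70%.

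**Step 4: what a fit does.** For (3, 0, 2, 11), ordinary logistic regression stopped with a singular matrix in one routine. In another it returned a log odds ratio of 23 with standard error about 17,000. The same table gives agreement of 14/16 = 88% (exact 95% CI 62% to 98%), kappa 0.67 and Fisher p = 0.018.

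**Step 5: odds ratio against agreement.** Tables (8, 0, 0, 8) and (2, 6, 0, 8) both have an infinite odds ratio. In the first, agreement is 16/16 and kappa is 1.00. In the second, agreement is 10/16 = 0.625, chance agreement is (8 × 2 + 8 × 14)/256 = 0.50, and kappa is 0.125/0.50 = 0.25.

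**Step 6: what no method rescues.** At 16 pairs and 10% positivity, 30-34% of tables have at least one constant marker. The chance of no tissue positives alone is 0.9^16 = 0.185.

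**The case against.** Several points on the other side have force.

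- **The failure depends on unknowns.** A reader might infer that the analysis will break on the data to be expected. The documents give no expected positivity or association, and 16 is the minimum, not a forecast: tissue is sought from all participants and 45 are enrolled. At 40-50% positivity and kappa of 0.4 or lower, the probability at 16 pairs is only 4-17%. This stands, so the point is conditional.
- **Agreement is not the stated question.** A reader might infer that CTCs are meant to replace tissue. The protocol promises only to correlate the two, and the listed secondary objective relates PD-L1 to PFS. The tissue is archival and the CTCs are drawn after chemotherapy, so disagreement could be biological. This stands: agreement measures are a useful addition, and no stated objective is broken without them.
- **The model might be different.** Section 9.0 also plans CTC counts and mRNA levels. With such a predictor the 2x2 probabilities would not apply, although separation could still occur. The yes/no reading of section 11.3 remains the more natural one.
- **Inference is left open.** It is tempting to say that the planned test would be meaningless. Section 11.3 names no test, and likelihood-ratio or exact inference still works with a single empty cell. The gap is that no sparse-data method is specified.
- **The work is exploratory.** True, and the plan has a descriptive fallback. That fallback is tied to biopsies, however, and stops where sparse tables are still common under low positivity or strong agreement.

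**Conclusion.** The point holds conditionally, as a low-cost improvement. If PD-L1 positivity is about 20% or lower, or if tissue and CTC status agree strongly, ordinary logistic regression near the planned threshold has roughly an even chance or worse of giving no finite odds ratio. At 40-50% positivity with moderate or weak association the risk is small. By 40-45 pairs it mostly fades, except at positivity near 10% or with agreement as strong as kappa 0.8. The number of pairs may be below 16 even when the biopsy count is not, because a pair also needs an evaluable CTC result. These figures rest on assumed positivity, equal in the two sources, and on assumed association. Separately, an odds ratio does not measure agreement at any sample size. The primary endpoint and the sample size are untouched.

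**What to change.** In section 11.3:

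1. Report the 2x2 table of tissue PD-L1 against baseline CTC PD-L1 (cycle 1 day 1, before dosing) with Fisher's exact test. This also settles which of the three draws is used.
2. Add Cohen's kappa, and positive and negative percent agreement with exact confidence intervals.
3. If a regression model is kept, fit it by Firth or exact logistic regression.
4. Apply the small-sample rule for this comparison to evaluable tissue-CTC pairs.
5. If either marker shows no variation, report descriptively only; kappa, Fisher's test and penalised fitting are uninformative there too.

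The cost is a few lines in the SAP. No additional data or samples are needed. Precision will stay modest: 12 of 16 in agreement is 75% with an exact 95% interval of 48% to 93%.
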